#### 4.2 Date of first and last administration of study drug

The date of first administration of study drug is defined as the baseline date.

The date/time of last administration of study drug is defined as the Date of last treatment administration as per End of treatment eCRF form. This value has to be consistent with IMP Administration information recorded on the corresponding eCRF forms. In case of different dates, the latest will be used as treatment end.

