#### 7.5 Sub-group analyses

Subgroup analyses of primary and secondary endpoints will be performed on the following subgroups of baseline characteristics:

- Age class (*Median*, *Median*).
- Race.
- Ethnicity.
- Gender.

Within each subgroup level, descriptive in nature analyses will be performed on:

- Schirmer I test.
- SANDE global, frequency and severity scores.
- NEI scale.

- TFBUT.
- IDEEL questionnaire.

at each available timepoints by means of descriptive statistics.

In case of continuous measures, analyses will be provided for baseline visit, each post-baseline visit, and their change from baseline. Comparisons between treatments will be performed using twosample t-test (assuming unequal variances) or, if the required assumptions are not met, the twosample Mann–Whitney U test will be used. Assumption of normal distribution of endpoints for continuous data will be assessed by a visual inspection of distribution.

In case of categorical variables, the Fisher's Exact test will be provided in addition to summary description.

Statistical tests for interaction (between subgroup variable and treatment arm) will be performed before investigating further subgroups: analyses of primary endpoints will be performed using regression models including treatment, subgroup variable and their interaction as covariate. If the interaction between subgroup variable and treatment arm is statistically significant at 15% nominal level in at least one regression model, then subgroup analysis will be performed.

Variables that may be evaluated after test for interaction are:

- Region (Europe, US),
- Sjögren's syndrome (primary, secondary), where "primary" is defined as a confirmed diagnosis of Sjögren's syndrome while "secondary" as other autoimmune disease known to induce Sjögren's Dry Eye Disease,
- Medical history,
- Concomitant medication.

Subgroup levels may be pooled to have an adequate number of subjects per strata to perform the analysis. Decision on pooling will be taken during the Blind Data Review Meeting (BDRM) before data base lock.

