#### 8.6 **Prior and concomitant medications**

A medication is defined:

- "Prior medication" if taken and stopped prior to first dose of study treatment.
- "Concomitant medication" if taken after the first dose of study treatment.

according to the available parts of the medication dates (see Table 7). In case of missing information not directly allowing allocation to either of the two above categories of medications, the medication will be considered as concomitant.

Prior and/or concomitant medications will be coded using World Health Organization Drug Dictionary and reported in separate tabulations. Frequency distributions and percentages will be summarized by treatment, type (Ophthalmic and Non-Ophthalmic), by Anatomical Main Group (1st level of the Anatomical Therapeutic Chemical (ATC) classification), Chemical Subgroup (4th level of the ATC classification) and Preferred Name.

Subjects taking more than one medication classified in the same category will be counted only once.

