#### Table 7: Algorithm for Prior/Concomitant medications

| MEDICATION START DATE | MEDICATION STOP DATE | RULE for prior or concomitant categorization   |
|-----------------------|----------------------|--|
| Known                 | Known                | If medication stop date < date of first dose of IMP, assign as prior   |
|                       |                      | If medication stop date >= date of first dose of IMP, assign as concomitant  |
|                       | Partial              | Impute medication stop date as latest possible date (i.e. last day of month if day unknown or 31 st December if day and month are unknown), then: |
|                       |                      | If medication stop date < date of first dose of IMP, assign as prior   |
|                       |                      | If medication stop date >= date of first dose of IMP, assign as concomitant  |
|                       | Missing              | Assign as concomitant  |
|                       |                      |  |
| Partial or Missing    | Known                | If medication stop date < date of first dose of IMP, assign as prior   |
|                       |                      | If medication stop date >= date of first dose of IMP, assign as concomitant  |
|                       | Partial              | Impute medication stop date as latest possible date (i.e. last day of month if day unknown or 31 st December if day and month are unknown), then: |
|                       |                      | If medication stop date < date of first dose of IMP, assign as prior   |
|                       |                      | If medication stop date >= date of first dose of IMP, assign as concomitant  |
|                       | Missing              | Assign as concomitant  |

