| Table 14.2.5.4.2 Absolute values and change from baseline in IDEEL Dry eye Treatment satisfaction & Bother module at each timepoint. Full analysis set  | x   | x              |
| Table 14.2.5.4.3 Absolute values and change from baseline in IDEEL Dry eye Symptom bother module at each timepoint. Full analysis set   | х   | x              |
| Table 14.2.5.5 Absolute values and change from baseline in Cornea and conjunctiva vital staining with fluorescein (NEI scale) at each timepoint. Full analysis set  | x   | x              |
| Table 14.2.5.6 Absolute values and change from baseline in TFBUT at each timepoint. Full analysis set   | х   | x              |
| Table 14.2.6.1.1 Subgroup evaluation: Schirmer I test (without anesthesia) >10mm/5min at week 4 - Treatment by region interaction- Logistic regression model - Multiple imputation. Full analysis set                               |     | x              |
| Table 14.2.6.1.2 Subgroup evaluation: Schirmer I test (without anesthesia) >10mm/5min at week 4 - Treatment by Sjögren's syndrome interaction- Logistic regression model - Multiple imputation. Full analysis set                   |     | x              |
| Table 14.2.6.1.3 Subgroup evaluation: Schirmer I test (without anesthesia) >10mm/5min at week 4 - Treatment by medical history interaction-
Logistic regression model - Multiple imputation. Full analysis set                   |     | x              |
| Table 14.2.6.1.4 Subgroup evaluation: Schirmer I test (without anesthesia) >10mm/5min at week 4 - Treatment by concomitant medication interaction- Logistic regression model - Multiple imputation. Full analysis set               |     | x              |
| Table 14.2.6.2.1 Subgroup evaluation: Change from baseline in the global SANDE score at week 12 - Analysis of Covariance (ANCOVA) -
Treatment by region interaction- Multiple imputation. Full analysis set                      |     | x              |
| Table 14.2.6.2.2 Subgroup evaluation: Change from baseline in the global SANDE score at week 12 - Analysis of Covariance (ANCOVA) - Treatment by Sjögren's syndrome interaction- Multiple imputation. Full analysis set             |     | x              |
| Table 14.2.6.2.3 Subgroup evaluation: Change from baseline in the global SANDE score at week 12 - Analysis of Covariance (ANCOVA) -
Treatment by medical history interaction- Multiple imputation. Full analysis set             |     | x              |

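### The concomitant-medication subgroup mixes drugs in use at baseline with drugs started after randomisation, so treatment effects within its levels can be biased

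*SAP*

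**What the plan says.** SAP 7.5 has two lists of subgroup factors. Age class, race, ethnicity and gender form the first, for which analyses "will be performed on the following subgroups of baseline characteristics". The second list (region, primary or secondary Sjögren's, medical history, concomitant medication) is introduced by "Variables that may be evaluated after test for interaction are". For the second list, a model with treatment, factor and their interaction is fitted to the primary endpoints, and a subgroup analysis follows if the interaction "is statistically significant at 15% nominal level in at least one regression model". SAP 15.1 lists the resulting tables for the final analysis: 14.2.6.1.4 for Schirmer I at week 4 ("Treatment by concomitant medication interaction- Logistic regression model - Multiple imputation") and 14.2.6.2.4 for SANDE at week 12.

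SAP 8.6 calls a medication concomitant "if taken after the first dose of study treatment". Table 7 applies this through the stop date: "If medication stop date >= date of first dose of IMP, assign as concomitant". Where information is missing and the category cannot be decided, "the medication will be considered as concomitant". For the reference date, SAP 4.2 states: "The date of first administration of study drug is defined as the baseline date".

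Protocol 3.3 lets systemic treatment change throughout the study and allows other topical treatments, at the physician's discretion, from week 12 to week 24. SAP 6.2 and 7.9 plan a single database lock at the end of the study, so medication started as late as week 24 will be in the analysis data.

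**The concern.** A subgroup comparison is protected by randomisation only if membership is settled before treatment can influence it. Under Table 7 a patient can become a concomitant user at any time up to the end of follow-up. A patient with a poor week 12 SANDE score who is then given a new topical drug is classed as a user in the analysis of that same score, so membership can follow from the outcome it is meant to explain.

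If cenegermin relieves symptoms, fewer cenegermin patients should need something extra. Those who do are then a more strongly selected, worse-off group than the vehicle patients who add medication. Users are not comparable between arms, and neither are non-users. What is at stake is a reader taking the within-level effects as evidence that cenegermin works less well, or equally poorly, in patients with or without other medication.

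**Working it through.** **1. Does any text restrict the factor to baseline use?**

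| Place | Content | Consequence |
|---|---|---|
| SAP 7.5, first list | Described as baseline characteristics | Does not govern the second list |
| SAP 7.5, second list | Concomitant medication named without classes, levels or time limit | Falls back on the general definition |
| SAP 8.6 and Table 7 | Stop date on or after first dose; unclear cases default to concomitant | Includes drugs ongoing at baseline and drugs started later |
| SAP 4.2 | First dose is on the baseline date | Everything from Visit 1 onward counts |
| Protocol 3.3 | New topical drugs allowed from week 12 to week 24 | Membership can be set after both co-primary time points |

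Nothing in either document narrows the factor to medication in use at Visit 1.

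**2. The plan's own figures, used as inputs.** SAP 5 gives 72 evaluable patients (36 per arm), a SANDE difference of 10 and an SD of 12. The standardised difference is 10 / (12 × √(2/36)) = 3.536. Normal power is Φ(3.536 − 1.960) = 94.2%, or 93.7% with the t distribution, against 94.1% stated. The plan gives no figure for the subgroup analysis.

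**3. How often the screen opens by chance.** With no true interaction, and taking the two endpoint tests as independent, one interaction term tested on both endpoints passes with probability 1 − 0.85² = 27.8%.

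**4. Illustration of the bias (assumed model).** Let Z be the SANDE change divided by 12, with negative values better. Z is normal with SD 1 and mean 0 on vehicle, and with mean −10/12 = −0.833 on cenegermin. Every patient has the same true benefit of 10 points. A patient becomes a user if Z + k·u > 0.2, where u is independent standard normal noise. A smaller k means that symptoms drive use more strongly. Write S = √(1 + k²) and a = (0.2 − mean)/S. Then:

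- share of users = 1 − Φ(a)
- mean change in users = 12 × [mean + φ(a) / (S × (1 − Φ(a)))]
- mean change in non-users = 12 × [mean − φ(a) / (S × Φ(a))]

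For k = 0.7, S = 1.221:

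| | Vehicle | Cenegermin | Apparent benefit |
|---|---|---|---|
| a | 0.164 | 0.847 | |
| Share of users | 43% | 20% | |
| Mean change, users | +8.9 | +3.8 | 5.1 |
| Mean change, non-users | −6.8 | −13.4 | 6.6 |

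A simulation of 4,000 trials with 36 per arm gave 5.1 in users and 6.5 in non-users. With medication status generated at baseline, independently of treatment, it gave 9.9 and 10.0.

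Varying k shows the range. With k = 0.5 the apparent benefits are 4.1 (users) and 6.0 (non-users). With k = 2 they are 8.6 and 8.9. The estimates therefore run from about 4 to 9 points against a true 10.

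**5. Two boundary checks.** With no treatment effect, a is the same in both arms, so shares and means are equal and the bias is zero. The simulated rejection rate of the interaction test at the 15% level was about 13% to 15%, close to nominal, because the estimates in both levels shrink in the same direction.

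**The case against.** The opposing case has real weight.

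- **The window before week 12 is narrow.** Until then, topical treatment is limited to cyclosporine or its class and sponsor-supplied artificial tears (Protocol 3.3 and 5.6), and tears have their own form and analysis (SAP 9.3 and Table 3). Systemic changes are allowed, but they serve the autoimmune disease, and Protocol 2.3.1 describes systemic absorption of cenegermin as negligible or undetectable. A strong difference between arms in early starts is therefore not obvious. This stands. It does not remove drugs started after week 12, which Table 7 still counts.
- **The factor is mixed, not purely post-randomisation.** Drugs started before randomisation and still in use also count. Topical cyclosporine or a same-class drug is an entry criterion, so a plain user/non-user split would hardly separate patients. The split in the illustration is an assumption, because the SAP defines no levels. This stands, and it is a second reason to specify the factor.
- **The analysis is exploratory.** The interaction tables are planned, the subgroup analysis is conditional, and pooling of levels is decided at the blind review. This stands.

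Three stronger readings are tempting and are not supported. A reader might infer that the SAP breaks its own restriction to baseline characteristics, but that phrase introduces only the first list. A reader might infer that the bias pushes the interaction through the 15% screen, but the rejection rate stayed near nominal in the setups examined. Other setups could differ, and the documents give no ground for assuming one. A reader might also infer bias even if cenegermin has no effect. Under symptom-driven use, no effect means equal starting rates in expectation and no bias.

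**Conclusion.** The point holds as a minor one. As written, the factor lets treatment response decide subgroup membership, even after both co-primary endpoints have been measured, and its levels are undefined. The demonstrated harm is to the within-level treatment estimates: about 4 to 9 points where the truth is 10.

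That size rests on assumed inputs: a real and uniform treatment effect, a user/non-user split, and use driven by the symptom course to varying degrees. The documents do not say how strongly symptoms will drive new medication, so the range illustrates the bias and does not predict it. No co-primary test, step of the hierarchy, sample size or power figure depends on this factor.

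**What to change.** In SAP 7.5, for the subgroup analysis only, replace concomitant medication by medication in use at or before Visit 1: start date on or before randomisation and still ongoing at that visit. Name the medication classes and levels before unblinding, and state how records with a missing or partial start date are handled, since the present default classes unclear records as concomitant. Retitle Tables 14.2.6.1.4 and 14.2.6.2.4 to match. Report medication started after baseline descriptively by arm. Dropping the factor would also resolve the point.

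The definition in SAP 8.6 and Table 7 can stay as it is for the general medication summaries. The cost is SAP wording and two table titles. Prior and concomitant medications are already recorded at screening and baseline, with start and stop dates (Protocol 2 and 5.6), so no new data are needed.

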# 7.6 Interim analysis

No interim analysis is planned.

# 7.7 Data Monitoring Committee

No Data Monitoring Committee has been established.

#### 7.8 Handling of missing and incomplete data

All reasonable efforts will be made to reduce the rate of missing data. Investigators will be trained about the importance of patient retention and full data capture. Also, any reasonable attempts should be made by the investigators to emphasize continued subject's participation for the full duration of the trial.

Patients who discontinue the treatment will not be withdrawn from the study by default but will be asked to complete safety and efficacy observations as per the protocol, unless otherwise they withdraw their consent. Patients who discontinue study treatment and decide to remain in the study

by following the schedule of assessments and continuing to adhere to protocol requirements are defined as "retrieved drop-out" patients.

For the primary and key secondary analyses, missing data will be handled by means of Multiple Imputation using retrieve dropouts (MI-RD), as detailed in sections 10.1.2 and 10.2.2.

In addition, to further minimize missing data, if a patient cannot refer to the site for a planned followup visit, the investigator will try to obtain any relevant information from the patients, including documents/laboratory results available from local medical care.

The number of subjects with missing data will be presented under the "Missing" category. Missing values will not be included in the denominator count when computing percentages. When continuous data will be summarized, only the non-missing values will be evaluated for computing summary statistics.

For the analyses of parameters for which an independent blinded reading center may be involved per protocol, the following rules will be used:

- 1. If assessment from blinded reading center is available, such value will be used for the analysis.
- 2. If assessment form blinded reading center is not available, the corresponding evaluation (if any) from the site investigator will be used.
- 3. If both assessments (blinded reading center and site investigator) are not available, a statistical imputation method will be applied as described in this SAP.

Rules for handling missing data of IDEEL questionnaire are reported in section 12.3, according to the dedicated manual.

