#### 6.1. SCREENING AND RANDOMIZATION VISITS

During the screening visit (day -8) all procedures for will be performed. From the day of screening the patients will stop any kind of further ophthalmic treatment, except CsA or equivalent, until all of the final study evaluations have been completed, except preservative free artificial tears (wash out period from day -8 to baseline, Day 1 + 2). The wash out period should not be less than 8 days and more than 10 days. At the end of the screening period, patients meeting the entry criteria for this study will be randomized 1:1 and treated for 4 weeks with either cenegermin ophthalmic solution 20 mcg/mL TID or vehicle TID.

Slit lamp examination and the fluorescein staining (Corneal and/or Conjunctival staining with Fluorescein) will be performed at different time-points, as specified in the section 2 of "SCHEDULE OF EVALUATIONS" and procedure will be detailed on the informed consent form.

An independent Blinded Reading Center (RC) will also be used to assess the images collected at protocolspecified time points and sent to the RC as specified in the RC procedure manual.

The RC will provide instructions for the slit lamp photography and the fluorescein staining procedures.

	Day	Procedures/Assessments

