Visit 3 week 4	Day 28±2	
 
The following procedures will be performed (the below order is mandatory):
 
Pregnancy test for female patients of childbirth potential
 
Ocular examination of both eyes to be performed by the physician investigator: 
 
Assessment by SANDE questionnaire
 
Assessment of best corrected distance visual acuity (BCDVA)
 
External Ocular Examination
 
Schirmer test I (without anesthesia)
 
Slit-lamp examination (SLE) to assess the Eyelid - Meibomian glands, Eyelid
 
Erythema, Eyelid - Edema Lashes, Conjunctiva Erythema, Lens, Iris, Anterior Chamber, Corneal Horizontal Diameter
 
TFBUT
 
Ocular surface staining (NEI score - corneal and conjunctival fluorescein staining)
 
Schirmer Test II (with Anesthesia)
 
 
 
Assessment of compliance to treatment (from patient diary and IMP reconciliation from returned weekly boxes)
 
Concomitant ocular and systemic medications
 
Frequency of patient's artificial tear use during the last 2 weeks of treatment (to be reported in eCRF).
 
AE monitoring
 
Verify patient study medication dosing compliance
 
 
During visit 3, week 4, PI or delegate must check and collect the patient's diary concerning the treatment period and provide a new diary for the follow up period. At completion of the assessment the patient will be discharged and will be asked to return for the follow up visit on day 56±2 (Visit 4 week 8). The Investigator will dispense to the patients the preservative free artificial tears of equivalent) provided by Sponsor, to be self-administered three times dialy, one drop in both eyes during the first 4 weeks of Follow up. The PI or delegate has to explain to the patients that, only if strictly needed, they can administer an additional numbers of drops of Blink® Tears or equivalent, by documenting all information in the patient's diary.

At home	Days 28 ±2– 56 ± 2	
 
Recording any new or changes in concomitant medications (diary)
 
Recording any unusual medical conditions - AE monitoring (diary)
 
Artificial tears use during 4 weeks of FU (diary) Data will be recorded by the patient on the patient's diary.
 

	Day	Procedures/Assessments

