#### 4.5 Baseline

Baseline is defined as the last visit prior to and including date of the randomization visit (Visit 1). Unless otherwise specified, baseline values are defined as the measurements taken during this visit. In case of multiple measurements during baseline visit, the last assessment will be considered as baseline evaluation before start of treatment.

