#### 12. Derivations and date conventions

# 12.1 Variable derivation

#### Table 3: Variable derivation rules

| Parameter   | Calculation  |
|---|--|
| Screened  | A patient is considered screened if (s)he has "Has written Informed Consent been obtained?" = Yes AND "Date of Informed Consent Signature at screening" filled   |
| Screening failure   | A patient is considered screening failure if (s)he has "Screen Failure date" filled  |
| Enrolled  | A patient is considered enrolled if (s)he has been screened and (s)he is not a screening failure.  |
| Eligible eye  | Assuming that all the inclusion/exclusion criteria are met:  |
|   | 
 
If only one eye fulfills the criteria of Severe Sjögren's Dry Eye ("Which eye is diagnosed with Severe Sjögren's Dry Eye?" is answered with "Right Eye" or "Left Eye") than the selected eye will be the "eligible eye".
 
If both eyes fulfill the criteria of Severe Sjögren's Dry Eye ("Which eye is diagnosed with Severe Sjögren's Dry Eye?" is answered with "Both") than the eligible eye will be selected according to the following rank: 
 
the eye with lower Schirmer I score, otherwise
 
the eye with worse NEI score (cornea+conjunctival staining), otherwise
 
the eye with worse investigator's judgement ("Were there any clinically significant abnormalities noted?" Equal to yes for a specific eye), otherwise
 
the right eye.
 
 
 
 |
| Change from baseline  | Each change from baseline will be defined as difference between the value at each post-baseline assessment and the baseline value.   |
| Time since first diagnosis of Dry
Eye  | Randomization date - Date of diagnosis for eligible eye + 1  |
| Time since first diagnosis of
Severe Sjögren's Dry Eye                         | Randomization date - Date of diagnosis of Severe Sjögren's Dry Eye for eligible eye + 1  |
| Total number of drops in the
eligible eye taken during the
treatment period | Sum of Morning/Afternoon/Evening Number of times the IMP has been administered for the eligible eye between Randomization visit date and End of Treatment date, considering 1 drop each time (morning, afternoon, evening).  |
| treatment period  | (from the eCRF form "IMP Administration" forms)  |

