# 12.4 Corneal and Conjunctiva Vital Staining with Fluorescein (NEI scale)

Corneal staining total score is defined as the sum of scores from 5 corneal areas: Central, Superior, Temporal, Nasal, and Inferior. The score for each area ranges from 0 to 3. Thus, the corneal staining total score can range from 0 to 15.

The conjunctiva is divided into a superior paralimbal area, an inferior paralimbal area and a peripheral area with a grading scale of 0-3 and with a maximal score of 9 for the nasal and temporal conjunctiva. Thus, the conjunctival staining total score can range from 0 to 18.

Corneal and conjunctiva vital staining total score is the sum of corneal staining total score and conjunctiva total score.

Information from blinded reading center and site investigators will be used as described in section 7.8.

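### A patient's NEI change from baseline can be a reading-centre grade minus a site grade, which adds noise to a late key secondary endpoint and can misclassify 50% worsening

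*SAP*

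**What the plan says.** **Two sets of grades.** Protocol 6.1 states: "An independent Blinded Reading Center (RC) will also be used to assess the images collected". The time points are left to the reading centre's procedure manual, which is not among the documents. The site grades as well. The visit tables in Protocol 6.1 and 6.2 include NEI staining in the investigator's ocular examination, and the schedule in Protocol section 2 lists it at every visit from screening to week 16.

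**Choice of source.** SAP 7.8 ranks the sources assessment by assessment. First: "If assessment from blinded reading center is available, such value will be used for the analysis". Failing that, "the corresponding evaluation (if any) from the site investigator will be used". Only if both are missing is the value imputed. SAP 12.4 brings NEI under this rule: "Information from blinded reading center and site investigators will be used as described in section 7.8". SAP 7.9 declares the rule as a clarification relative to the protocol.

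**Change from baseline.** SAP Table 3: "Each change from baseline will be defined as difference between the value at each post-baseline assessment and the baseline value". The baseline definition in SAP 4.5 does not mention the grader either: "In case of multiple measurements during baseline visit, the last assessment will be considered as baseline evaluation before start of treatment".

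**Where NEI is used.** NEI change at weeks 4, 8 and 12 is key secondary endpoint 5 (tests 5.1 to 5.3 in SAP 10.2.2). Worsening of at least 50% in SANDE and/or NEI at week 4 is a secondary endpoint outside the ranked list, analysed descriptively under SAP 10.2.3. The NEI model in SAP 10.2.2.5 adjusts for gender, age class, baseline NEI, treatment, visit and treatment by visit. It does not adjust for grader source or site.

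**The concern.** A change score is meant to measure change in the eye. If the baseline grade comes from the reading centre and the week-4 grade from the site, any systematic or random difference between the two graders is counted as change. Nothing in either document requires matched sources, flags mixed pairs or plans an NEI analysis from a single source; the sensitivity analyses in SAP 10.1.3 cover the primary endpoints only.

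Two things are at stake. In key secondary endpoint 5, mixed pairs inflate the variance of change and so cost power. In the 50% worsening endpoint, a grader difference can create or hide an event. Entry requires an NEI score of only 3 or more, so the threshold can be as low as 2 points. Because that endpoint is an and/or composite, an NEI artefact alone is enough to make an event.

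**Working it through.** **The plan's own figures.** The documents contain no calculation about NEI or grader agreement. Their only design calculation is the co-primary power in SAP section 5, and it reproduces. With 36 patients per arm and one-sided alpha 0.025, 33% against 75% gives 96.3% (stated 96.3%); 10 points with SD 12 gives 94.2% by the normal approximation or 93.7% by the noncentral t (stated 94.1%). NEI does not enter it.

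**1. Tracing the rule on one hypothetical patient.** Suppose the eye does not change and the site grades 3 points above the reading centre.

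| | Baseline | Week 4 | Change |
|---|---|---|---|
| Reading centre | 6 | 6 | 0 |
| Site | 9 | 9 | 0 |
| SAP 7.8, week-4 reading-centre grade missing | 6 | 9 | +3, i.e. 3/6 = 50% |

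Either source alone gives no change. The plan's rule gives a worsening event.

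**2. Variance of NEI change.** All inputs are assumed, because the documents give none: SD of change 5 (variance 25), constant offset b of 2 to 4 points, share f of mixed pairs 10% to 30%.

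- Mixing one way only: a patient gains b with probability f, so the added variance is f·b² − (f·b)² = f(1−f)·b².
  - Low end: 0.1 × 0.9 × 4 = 0.36, and 0.36/25 = 1.4%.
  - High end: 0.3 × 0.7 × 16 = 3.36, and 3.36/25 = 13.4%.
- Both directions equally common: +b and −b each with probability f/2, mean zero, so the added variance is f·b².
  - Low end: 0.1 × 4 = 0.40, and 0.40/25 = 1.6%.
  - High end: 0.3 × 16 = 4.8, and 4.8/25 = 19.2%.

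Random disagreement between graders would add to this. The baseline covariate would absorb part of an offset that sits in the baseline value.

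**3. Power.** Take a test that would have 80% power with SD s. Under one-way mixing its power becomes Φ(2.802 × s/√(s² + f(1−f)b²) − 1.960). Over assumed ranges of s = 3 to 5, b = 1 to 3 and f = 5% to 30%, this runs from just under 80% down to 72%. The low end is s = 3, b = 3, f = 30%: √(9 + 0.21 × 9) = 3.3, then 2.802 × 3/3.3 − 1.960 = 0.587, and Φ(0.587) = 0.72.

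**4. The 50% threshold.** The smallest whole-point rise that counts is half the baseline, rounded up. The last column is the chance that a patient with no true change and a mixed pair is classed as worsened on NEI. It assumes a normal grader difference with offset 0 to +2 and SD 1 to 3, and a threshold half a point below the count shown.

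| Baseline NEI | Points needed | Chance of false worsening |
|---|---|---|
| 3 | 2 | 0.07 to 0.69 |
| 4 | 2 | not computed |
| 6 | 3 | 0.01 to 0.43 |
| 10 | 5 | 0.00 to 0.20 |
| 15 | 8 | 0.00 to 0.03 |
| 16 | 8 | not computed |

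The scale runs from 0 to 33 (15 corneal plus 18 conjunctival, SAP 12.4). The documents give no expected baseline.

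**5. A gap covering a whole visit in both arms.** Here f = 1, so f(1−f)·b² = 0. Every patient's change at that visit moves by the same b, and the shift cancels in the arm difference in means. It stays in each patient's own percentage change, so the 50% classification is still affected.

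**The case against.** The strongest reply is that the consequences are small. The reading centre is blinded, investigators are masked, and randomisation is stratified by site, so nothing suggests that reading-centre gaps differ by arm. NEI is tested only after both co-primaries and nine earlier key secondary tests (1, 2, 3 and 4.1 to 4.6) succeed. The worsening endpoint is descriptive. The source ranking is a declared choice, and all patient data will be listed. All of this stands and limits the weight of the point. It does not remove the defect, because no passage prevents a change score from crossing graders.

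Three stronger readings are tempting, and the documents do not support them.

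- *Biased treatment effect.* With one-way mixing the arm mean shifts by f·b, here 0.1 × 2 = 0.2 to 0.3 × 4 = 1.2 points. The shift becomes bias only if mixing differs between arms, and neither document gives reason to expect that.
- *A missing reading-centre visit undermines the NEI comparison.* Protocol 6.1 says the centre is used "to assess the images collected at protocolspecified time points and sent to the RC", which might suggest that some visits are never read. The documents do not show that, and step 5 shows that the comparison of means would survive it.
- *Contamination of the co-primary Schirmer result through the choice of eligible eye.* NEI breaks ties when Schirmer I is equal in the two eyes. That compares two eyes at the baseline visit and involves no change score. It arises only on a tie, and nothing shows that the two eyes would have different sources.

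**Conclusion.** The point holds as a minor one. Followed as written, SAP 7.8, 12.4 and Table 3 allow an NEI change that is partly a difference between graders. The expected effect is noise in tests 5.1 to 5.3 and non-differential misclassification on the 50% worsening endpoint, most easily at low baselines.

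The size cannot be read from the documents. The variance increases of about 1% to 13% and 2% to 19% rest on the assumed SD, offset and mixing rate, and would be close to nil if reading-centre grades are almost complete. The co-primary analyses, sample size and alpha are not shown to be affected.

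**What to change.** Settle the rule before database lock; the blind data review in SAP 7.10 is a natural place. NEI change is also among the key first results (Table 14.2.5.5), so choosing a source after unblinding would be hard to defend. Either of two changes to SAP 7.8 and 12.4 would do.

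- **One source per patient.** Use reading-centre grades throughout if they exist at baseline and at every analysed visit that the patient attended; otherwise use site grades throughout. Apply the chosen source to the baseline covariate, the changes, the imputation and the 50% worsening endpoint. Matching sources separately for each change would not be enough: it could give one patient two baselines and mixed sources within a single repeated-measures outcome.
- **Or keep the SAP 7.8 ranking** and add a site-only sensitivity analysis of NEI change and of the worsening endpoint. Site grading is scheduled at every efficacy visit, so the data should exist.

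In either case, flag the grade source in Listing 16.2.6.4 and report, by arm and visit, how many baseline and follow-up pairs are mixed under the SAP 7.8 ranking.

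Cost: SAP wording and a small derivation change. Under the per-patient rule, reading-centre grades go unused for any patient whose reading-centre series is incomplete, and different patients may still be graded by different sources, although no change crosses graders. The alternative costs a little more analysis work.
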